An overview of the pilot RCT and the randomization scheme is shown in the Figure below. After being consented, all HHAs will attend a virtual orientation session and virtual HF training course. Prior to the course, all HHAs will complete a baseline questionnaire (see attached survey document) and be randomized in a 1:1 ratio (T1). The training course will be conducted via Zoom and led by WCM investigators and VNS Health staff members. After taking the course, HHAs in both arms will take a short post-course questionnaire (to assess the two primary outcomes; knowledge and HF caregiving self-efficacy). HHAs randomized to the enhanced usual care arm will receive a just-in-time course refresher via their Care Connect app (self-driven educational content) prior to caring for their HF patient. HHAs randomized to the intervention will receive a just-in-time course refresher as well as an app training session from a Weill Cornell Medicine research assistant (overseen by [name] in computer science). HHAs in this arm will be encouraged to use the app when they have questions about their patient, want to access HF-related content, or need to communicate with the nurse. To reinforce their use of the use of the application chat features, they will receive "do not reply" text based notifications reminding them that the feature is there and can be used. Following the care of their first patient, HHAs in both arms will take a follow-up questionnaire. Each HHA will be involved in the study for 90 days. During that time, if the HHA is assigned to a new HF patient, they can continue participation although they will remain randomized to their original treatment arm to avoid contamination. De-identified data on HF patients cared for by the HHAs (demographics, clinical conditions, ED visits; 30-day/90-day readmissions; hospitalization; functional status; and quality of life) will be retrospectively collected by the VNS Health from intake/referral data and OASIS. HHAs will receive \$100 for participating; they will receive \$25 at trial start, \$25 following the completion of the heart failure training course and survey 2, \$25 following the 45-day (mid-study) interview, and \$25 following the final survey.

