Data to be Collected and Analyzed: The questionnaire (see attached document) will be administered using Research Electronic Data Capture (REDCap), a web-based, secure, data storage program at Weill Cornell Medicine at several time points during the study. A research assistant at Weill Cornell Medicine will export the de-identified data that is collected in REDCap to STATA, a statistical software package, for analysis. A data analyst at Weill Cornell Medicine will analyze this data under PI [name]'s supervision (IRB at WCM to safeguard this aspect of the project). App usage data from the mHealth app (intervention arm) will be monitored by [name] (Scientific adviser/collaborator from Cornell; health technology). After 90 days, data from the mHealth app will be extracted by [name] and the Care Connect team (that works with Partner's in Care) and transferred and stored on a secure server on a password-protected computer at Weill Cornell Medicine which is monitored by WCM ITS. This data will be analyzed by a data analyst at Weill Cornell under PI [name]'s supervision. Finally, data on the HF patients cared for by the HHAs in the trial (demographics, clinical co-morbidities, and outcomes [ED visits and 30-day readmissions, functional status]) will be extracted by the VNS Health programmer from the agency's clinical records and administrative data. This type of data collection is part of the agency's ongoing quality improvement activities and falls under the agency's routine admissions procedures with patients. Like many studies at VNS Health, the clinical outcomes will be extracted from the Home Health Outcome and Assessment Information Set (OASIS). Data will be de-identified and analyzed at VNS Health, under Site-PI [name] supervision. All OASIS data will be analyzed at VNS Health. At the end of the study, under [name] supervision, trial participants (HHAs, nurses) will be interviewed to assess their experience with the training course and mHealth app. Additionally, short, telephone-based interviews will be conducted with a sub-set of patients by [name]. These interviews will focus on their perspectives towards their HHAs, not about their medical care or their health, and will not last more than 30 minutes. They will be audio-recorded and professionally transcribed. Transcripts will be stored on a secure password-protected computer at WCM, which is monitored by WCM ITS. [name] will oversee the qualitative data analysis.

Brief Overview of Analytic Methods:

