efficacy scores by trial arm using paired t-tests for normally distributed data or Wilcoxon signed rank test for non-parametric data. We will examine the effect of randomization on the change in scores, using mixed linear regression models. Mixed-effects included a fixed effects categorical variable for time point (baseline/post-course/90 day), an indicator for study arm (control/intervention), a study arm by timepoint interaction and subject-specific random intercept. Primary analyses will be conducted using intention-to-treat, when appropriate. We will examine HHA characteristics across trial arms and adjust for covariates that are imbalanced ($p < 0.10$). We will conduct the same analyses for the secondary outcomes (burnout and job satisfaction). For patient outcomes, we will perform exploratory analyses to determine the effect of the intervention on ED visit rates and hospitalization rates; and functional status, using Poisson mixed effects regression models to account for clustering of patients within HHAs. To measure what would have occurred with usual care (e.g. without enhanced usual care or the intervention), we will assess ED visit rates and 30-day readmission rates among HHAs 90 days before vs. 90 days after randomization, adjusting for clustering of patients within HHAs, and stratified by trial arm. Analyses will be done using STATA statistical software.

Power and Sample Size: To detect minimal clinically important differences (MCID) for both outcomes (a 1-point change in mean score on the Dutch HF Knowledge Scale; an 8-point change in mean score on the HF caregiving self-efficacy), with 80% power, α at 0.05, and conservatively allowing for 15% attrition, we will need 104 HHAs (52 per arm). The overall α at 0.05 enables testing of two hypotheses using Bonferroni's method. Consistent with the goals of this study (to assess feasibility and acceptability of the intervention and obtain preliminary effectiveness estimates on primary outcomes), we have not powered our study on secondary outcomes or on patient outcomes. These calculations were done in Stata v13, College Station, TX.

Statement of the Risks/Benefits for the Study Subjects:

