The HHAs will receive a HF training course and will perform routine caregiving tasks while caring for HF patients in this study. Those in the intervention arm, will also have the opportunity to engage (electronically) with their supervisors to ask clinical questions, rather than usual care (trying to reach them by phone). The questions will be asked via a secure, HIPAA protected function on the mHealth app (Care Connected) (monitored by [name], adviser in health technology, and the Care Connect team) and no identifying information will be used. All participants will be asked to complete questionnaires at 4 time points during the trial, which contain no identifying information. Although every reasonable effort has been taken, confidentiality during Internet communication procedures cannot be guaranteed and it is possible that additional information beyond that collected for research purposes may be captured and used by others not associated with this study. The VNS Health and Weill Cornell Medicine take the privacy and security of study data seriously. To preserve confidentiality, data will be collected and stored at Weill Cornell Medicine on secure servers monitored by Weill Cornell Medicine ITS. Data will only be available to authorized individuals on the study team. When necessary, data will be sent over private connections secured by the WCM ITS. Furthermore, data sets will be encrypted and reported in aggregate form only. VNS Health study staff will have initial access to patient-level data in order to merge data sources and identify the patient cohort of interest; and to link a home health aide to a specific patient for intervention workflow processes. The outcome file that will be shared with Weill Cornell study staff will include a Study ID, the age of the patient, and information on hospitalizations and ED visits within 90 days of the start of the intervention. Both VNS Health and Weill Cornell study staff will have access to the communication (via the Chat feature in Care Connect) between the home health aide and the supervisory nurses. It is possible that patient name and other identifiers will be included within this communication. At both sites all data will be secured in password protected, HIPAA secured data systems. Sharing of data across sites will be done through the VNS Health approved email encryption process and/or through the approved MSTEams application. For the entire study, data will be reported in aggregate form only. PI [name] will ensure that all study team members will be trained thoroughly in the need to maintain confidentiality and no information collected will be used for any purpose other than those stated in the informed consent form. Rules for handling confidential data and security of patient information will be strictly abided by all study team members in charge of handling data.

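### The exploratory patient-outcome models use no start-of-care patient covariates, so differences in patient mix between arms can distort or blur the comparison

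*Combined protocol and SAP*

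**What the plan says.** Study Design randomises aides 1:1 before the training course. The refresher follows, ahead of the aide's care of the HF patient. Later patients can also join: "if the HHA is assigned to a new HF patient, they can continue participation although they will remain randomized to their original treatment arm". The eligibility text under Sample Selection/Data Sources takes aides who are assigned HF patients, so some pairings may precede randomisation.

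The section on privacy and confidentiality gives VNS Health study staff access to patient-level data, among other reasons "to link a home health aide to a specific patient for intervention workflow processes". No section says how patients are allocated to aides, or whether those who allocate them know the arm.

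The Outcome analyses section plans the patient comparison "using Poisson mixed effects regression models to account for clustering of patients within HHAs". It names no patient covariate. The adjustment rule reads "We will examine HHA characteristics across trial arms and adjust for covariates that are imbalanced", with a threshold of p < 0.10, and the balance tests under Baseline analyses concern the aide questionnaire. A second analysis compares ED visit and 30-day readmission rates in the 90 days before and after randomisation, separately by arm, again adjusting only for clustering.

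Table 1 lists baseline and follow-up sources for the aide scales, but only follow-up administrative data for patient functional status. Patient demographics and co-morbidities are nevertheless extracted, and Data to be Collected and Analyzed states that "the clinical outcomes will be extracted from the Home Health Outcome and Assessment Information Set (OASIS") and that all OASIS analysis stays at VNS Health.

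**The concern.** The plan treats its two levels differently. Aide outcomes get a baseline measurement, a time-by-arm model and an imbalance rule. Patient outcomes get a term for clustering, which addresses the standard errors but not who the patients were when care began.

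Patients recently discharged after heart failure differ widely in risk and function. If one arm's aides happen to care for sicker patients, or are given them, the between-arm difference carries that gap. For functional status, end points are compared with no stated starting point. Exploring patient outcomes is part of the stated purpose, so a signal, or the lack of one, could influence the decision on a larger trial. The data that would help are in large part already being extracted.

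**Working it through.** **The plan's own figure.** The plan gives no sample size, rate or detectable difference for patient outcomes. Its 104 aides (52 per arm) serve the two aide-level outcomes. No SD is stated, so 104 cannot be reproduced forwards; 52 × 0.85 = 44.2 evaluable aides per arm is consistent with the 15% attrition allowance. It does not bear on this point.

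**Inputs.** From the documents: 52 aides per arm, and 25% readmission at 30 days (a national background figure for Medicare patients). Assumed: one patient per aide, half of control patients high-risk, high-risk patients at 2 to 3 times the risk of the others, no app effect, and a correlation r of 0.5 to 0.7 between start-of-care and follow-up function.

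**1. How large a gap can chance produce?** SD of the arm difference in high-risk share = √(2 × 0.5 × 0.5 / 52) = 9.8 points; 95% range ±19.2 points. A gap of 10 to 20 points is about one to two SDs.

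**2. Effect on readmission.** Low risk = 0.25 / (0.5 + 0.5 × RR); high risk = RR × low risk. With s the shortfall of high-risk patients in the app arm, its crude risk = (0.5 − s) × high + (0.5 + s) × low.

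- RR 2 (risks 0.167 and 0.333): s = 0.10 gives 0.233, ratio 0.93; s = 0.20 gives 0.217, ratio 0.87.
- RR 3 (risks 0.125 and 0.375): s = 0.10 gives 0.225, ratio 0.90; s = 0.20 gives 0.200, ratio 0.80.

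The shift is 1.7 to 5.0 points. Stratifying on start-of-care risk returns a ratio of 1.00. For scale, the SE of the difference is √(2 × 0.25 × 0.75 / 52) = 8.5 points, a 95% half-width of 16.6 points.

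**3. Effect on functional status.** With a start-of-care gap of b SD, the unadjusted follow-up difference is r × b. For b = 0.2 this is 0.10 to 0.14 SD; for b = 0.4 it is 0.20 to 0.28 SD. The chance SE of b is √(2/52) = 0.196 SD, so 0.2 is about one SE. Conditioning on the starting value removes the difference and leaves 1 − r² = 0.75 to 0.51 of the patient-level variance. This is linear-model arithmetic. The plan names a Poisson model for function too, so the gain there is only indicative.

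**4. Recovery between concurrent arms.** If both arms improve by the same amount, that amount subtracts out and contributes 0. It enters only if mix, time since discharge or assessment timing differs by arm. Assuming 0.5 SD recovery over 60 days, a timing gap of 7 to 14 days would give 0.5 × 7/60 = 0.06 to 0.5 × 14/60 = 0.12 SD.

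**5. Recovery in the before/after comparison.** Let the daily event rate in the first 30 days be k times the later rate, and let f be the share of patient time in that early period. With no true effect, the rate ratio is (1 + f_after(k − 1)) / (1 + f_before(k − 1)).

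- k = 2: f from 0.50 to 0.33 gives 1.33/1.50 = 0.89; f from 0.60 to 0.20 gives 1.20/1.60 = 0.75.
- k = 4/3: the same shifts give 0.95 and 0.89.

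This illustration fits ED visits best. Table 1 counts 30-day readmission from the start of the home care episode, which partly fixes the clock for that outcome.

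**The case against.** The strongest reply is that these outcomes are exploratory and expressly unpowered, that the section is headed as a brief overview, and that a covariate list missing from an overview does not rule out adjustment. This stands, and it limits the severity.

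It can also be said that the illustrated gaps are no larger than chance produces. A 10 point gap in high-risk share is about one SD, and the resulting 1.7 point shift (RR 2) is small against an SE of 8.5 points. Chance imbalance of that size is already reflected in the confidence interval. This too stands: the figures show how far mix can move the estimate, and do not demonstrate bias. Adjustment then mainly buys precision, and guards against an unlucky split.

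Three stronger readings are tempting, and the documents do not support them.

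- A reader might infer that natural post-discharge recovery could pass as an app effect in the two-arm comparison. Recovery shared by concurrent arms cancels there.
- A reader might infer from the linkage sentence that study staff choose patients by arm. That sentence explains data access. The risk section's statement that standard care is not disrupted fits ordinary dispatch. Assignment after randomisation causes selection bias only if it depends on arm; otherwise randomisation protects the mix in expectation.
- A reader might infer that the file sent to Weill Cornell (study ID, age, hospitalisations, ED visits) prevents adjustment. The text does not say the file is limited to those fields, and OASIS analysis stays at VNS Health in any case.

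**Conclusion.** The point holds as a limited one. The patient-outcome models account for clustering only, no patient start-of-care covariate or starting functional value is named, and patients are largely linked to aides after randomisation. Differences in mix can therefore distort or blur the between-arm comparison. Selection by arm is an open question, because the plan is silent on it.

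On the assumptions above, gaps of one to two chance SDs in high-risk share correspond to risk ratios of 0.93 to 0.80 with no app effect. A 0.2 SD gap in starting function leaves 0.10 to 0.14 SD at follow-up. Only the 25% rate and the 52 per arm come from the documents; the risk ratios, correlations and shares are assumed. More than one patient per aide would change the standard errors.

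Recovery is a direct threat only in the within-arm before/after comparison, which would in any case reflect the training with or without the app rather than the app alone. Severity: an optional improvement to an exploratory, unpowered analysis.

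**What to change.** In the patient models run at VNS Health:

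- Prespecify a short list of start-of-care covariates, included regardless of any imbalance test: age, a co-morbidity summary and, if it can be retrieved from OASIS, start-of-care functional score.
- Analyse follow-up function conditional on its start-of-care value.
- Tabulate patients' start-of-care characteristics by arm.
- Describe how patients are assigned to aides and whether those who assign them know the arm. The plan should report what happens, and not simply assert that dispatch is neutral.
- State that the before/after comparison is open to differences in time since the start of care, which these covariates do not remove.

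Cost: protocol wording and a few more fields in an extract already planned. The functional adjustment depends on a start-of-care OASIS score being available for these patients, which the documents do not confirm. Events are few: 0.25 × 104 = 26 readmissions if there are 104 patients at the assumed 25% risk, so arm plus three covariates leaves 26/4 = 6.5 events per term. The list should stay short.

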Title of the Project: Leveraging Home Health Aides to Improve Patient Outcomes in Heart Failure: A Pilot Randomized Controlled Trial

NCT #: NCT04239911

Document Date: 4/22/2025

Study Title: Leveraging Home Health Aides to Improve Outcomes in Heart Failure: Pilot Randomized Controlled Trial

Principal Investigator: [name], MPH, MS

Funder: National Heart, Lung, and Blood Institute (K23HL15060)

VNS HEALTH – Research Protocol

Background: Heart failure (HF) affects 6 million people in the U.S. and costs over 30 billion dollars per year. There are 1 million HF hospitalizations per year, and 25% of Medicare beneficiaries admitted for HF are readmitted within 30 days. Previous interventions to reduce HF readmissions have had mixed results, perhaps in part because they did not involve home health aides (HHAs). After a HF hospitalization, a third of Medicare beneficiaries are discharged home with home care services, which may include support from HHAs. Unlike physicians or visiting nurses, HHAs are with patients on a near-daily basis, sometimes up to 24 hours per day. However, my prior qualitative research suggests that HHAs do not receive HF-specific education and are not confident caring for HF patients. In addition, my prior work has shown that HHAs experience difficulty reaching their supervising nurses (at their home care agencies) when they have questions or need help managing patients in the home. As a result, HHAs often resort to calling 9-1-1 and subsequently bringing their patients to the emergency department (ED). While some ED visits may be clinically appropriate, many may be avoidable. Interventions that can optimize and improve the experience of HHAs caring for the HF patients have the potential to improve HHAs own self-efficacy but also patient outcomes.

To that end, we have developed a HF intervention for HHAs comprised of a) remote classroom education on HF and b) an mHealth app containing HF educational content and a messaging application that connects HHAs and their nurse supervisors. This intervention requires feasibility testing, as well as preliminary testing of its acceptability and effectiveness among HHAs.

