Outcomes	Validated Scale	Description	Data source
Primary Outcomes (HCWs)			
HF knowledge	Dutch HF Knowledge Scale	15 item scale measures HF knowledge in general, knowledge of HF treatments, and HF symptom recognition. Scores range from 0-15, with higher scores indicating higher HF knowledge.	Baseline and follow-up questionnaires
HF caregiving self-efficacy	Caregiver Contribution to Self-Care in HF Index (CC-SCHFI)	22-item scale measures caregivers' 1) contributions to HF maintenance; 2) contributions to HF management; and 3) HF caregiving self-efficacy (confidence). Each of these 3 subscales are scored independently. The third sub-scale (self-efficacy) will be the main outcome. Self-efficacy scores range from 0-100, with higher scores indicating greater self-efficacy.	Baseline and follow-up questionnaires
Secondary Outcomes (HCWs)			
Intention to Leave	Turnover intention scale	2-item scale measures workers' intentions of 1) leaving their current job (at their agency) and 2) searching for a new job (in another field) in the next year	Baseline and follow-up questionnaires
Job satisfaction	Work Domain Satisfaction Scale	This 5-item scale measures 1) job satisfaction among care workers; and 2) examines the associations with work environment factors, work stressors, and health issues. Scores range from 5-20, with higher scores indicating stronger satisfaction.	Baseline and follow-up questionnaires
Other Specified Outcomes			
Communication practices	Preventable 911 Calls	2 novel questions “I have called 911 when that could have been prevented if I had been able to reach my supervisor/the nurse.” And “I have called 911 when that could have been prevented if my supervisor and I had been able to reach the client's doctor.”	Baseline and follow-up questionnaires

		Responses for both included a 7-point likert scale of: very strongly disagree, strongly disagree, disagree neutral, agree, strongly agree, very strongly agree. Both questions dichotomized into “agree”, “strongly agree”, and “very strongly” vs. all other responses.	
Patient Outcomes (exploratory)			
30-day readmission; 90-day (all-cause)	N/A	A readmission to any hospital (for any reason) at 30-days after start of home care episode.	Follow-Up VNS Health administrative data
Emergency department visit (all-cause)	N/A	A visit to the emergency department of any hospital (for any reason) after start of home care episode	Follow-Up VNS Health administrative data

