Functional status	N/A	Activities of daily living, physical function	Follow-Up VNS Health administrative data
Hospitalization	N/A	A hospitalization to any hospital (for any reason) during the study period	Follow-Up VNS Health administrative data
Quality of Life	Cardiomyopathy Questionnaire (Kansas City) [KCCQ-12]	The Kansas City Cardiomyopathy Questionnaire (KCCQ-12) is a 12-item self-administered questionnaire adapted from the KCCQ, a 23-item self-administered questionnaire which independently evaluates patient's perceptions of their health status with particular focus on heart failure symptoms, impact on physical and social function, the disease's impacts on their quality of life (QOL) within a 2-week recall period.	Interview

Sample Selection/Data Sources: English and Spanish speaking HHAs assigned to care for adults admitted to home care with a primary diagnosis of HF during the study period will be eligible. According to our preliminary estimates, VNS Health HHAs care for 2,280 new HF cases per year, for an estimated 4,560 cases during the 2-year trial. HHAs with less than 1 year of job experience will be excluded. We expect 400 HHAs will need to be screened to reach the goal of 104. Additionally, 12 nurses will be recruited (convenience sampling) to participate in pilot RCT.

HHAs will be studied for 90-days. HHAs will be asked to complete an electronic survey 3 times during the study; first before the virtual orientation session at the time of recruitment (beginning

of the trial; prior to randomization); second after receiving the HF training course; and lastly at 90 days after the completion of the training course.

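### The plan does not say whether ED visits, hospitalizations and readmissions are any-event or count outcomes; if they are yes/no, the planned Poisson mixed model overstates the standard errors

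*Combined protocol and SAP*

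**What the plan says.** Table 1 describes three hospital-use outcomes, all labelled exploratory:

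- ED visit: "A visit to the emergency department of any hospital (for any reason) after start of home care episode".
- Hospitalization: "A hospitalization to any hospital (for any reason) during the study period".
- Readmission: "A readmission to any hospital (for any reason) at 30-days after start of home care episode". A 90-day version is named in the same row but not described.

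None of these entries says whether the patient-level variable is any event versus none, or the number of events.

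Under Brief Overview of Analytic Methods (Outcome analyses), the between-arm patient analysis covers "ED visit rates and hospitalization rates; and functional status", "using Poisson mixed effects regression models to account for clustering of patients within HHAs". No robust variance, exposure term or dispersion term is given. Readmission is not in that sentence, although the same section lists 30-day readmissions among the patient outcomes on which the intervention effect will be assessed. Readmission rates reappear in the next sentence, in a comparison of the 90 days before and after randomization. That comparison adjusts for clustering but names no model.

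The only event frequency in the document is in the Background: "25% of Medicare beneficiaries admitted for HF are readmitted within 30 days". The Power and Sample Size section says the study is not powered for patient outcomes.

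**The concern.** A Poisson model takes the variance of the outcome to equal its mean. That suits counts. For a yes/no outcome with probability p, the variance is p(1-p), which is smaller than p, so model-based standard errors come out too large. The usual remedy is a sandwich variance, and none is mentioned. A random intercept for the aide does not help, because it can only add variance to the Poisson variance.

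At stake is the width of the confidence intervals for ED use and hospital use. The study purpose says effects on ED visits and 30-day readmissions will be explored. In an exploratory analysis the interval is the main thing a later trial can use, and needless width makes a real signal easier to miss. With the coding unstated, a reader also cannot tell whether the reported ratio will be a risk ratio or a rate ratio.

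**Working it through.** The plan gives no figure for the patient outcomes, so there is none to reproduce.

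**Inputs.** From the documents: 52 aides per arm, and p = 25% (30-day readmission, national). Assumed: p = 10% and 40% as a range; 1 to 3 patients per aide, since the Study Design section says only that "if the HHA is assigned to a new HF patient, they can continue participation"; and a within-aide correlation (ICC) of 0 to 0.10.

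**Step 1, yes/no coding, no clustering.** With n patients per arm and the same p in both arms, the variance of the log ratio is

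- Poisson, model-based: 2/(np)
- actual (binomial): 2(1-p)/(np)

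so the SE ratio is 1/sqrt(1-p).

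| p | SE ratio | True type I error of a nominal 5% test |
|---|---|---|
| 10% (assumed) | 1/sqrt(0.90) = 1.054 | 3.9% |
| 25% (documented, readmission) | 1/sqrt(0.75) = 1.155 | 2.4% |
| 40% (assumed) | 1/sqrt(0.60) = 1.291 | 1.1% |

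The last column is 2[1 - Φ(1.96 × SE ratio)].

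With one patient per aide, n = 52 and p = 25%, np = 13. The Poisson SE is sqrt(2/13) = 0.392 and the actual SE is sqrt(1.5/13) = 0.340. The 95% interval multiplies and divides the ratio by exp(1.96 × 0.392) = 2.16 instead of exp(1.96 × 0.340) = 1.95.

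**Step 2, clustering.** With m patients per aide, the actual variance is multiplied by 1 + (m-1)ICC. In simulations of yes/no data with a Poisson random-intercept model (600 runs per setting), the intercept SD was estimated near zero in 90% to 100% of runs, even at ICC 0.10. The reported SE therefore stays close to the plain Poisson SE, and the ratio is about 1/sqrt((1-p)(1 + (m-1)ICC)). At ICC 0.10:

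- m = 2: 1/sqrt(0.75 × 1.1) = 1.10 at p = 25%; 1/sqrt(0.60 × 1.1) = 1.23 at p = 40%.
- m = 3: 1/sqrt(0.75 × 1.2) = 1.05 at p = 25%; 1/sqrt(0.60 × 1.2) = 1.18 at p = 40%.

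Those simulations gave an excess of about 3% at p = 25% and 12% to 19% at p = 40% for 2 to 3 patients per aide at ICC 0.10. The Monte Carlo error of each ratio is about 1/sqrt(2 × 600) = 3%. A separate simulation with 1 to 3 patients per aide, over ICC 0 to 0.10, gave 9% to 18% at p = 25% and 22% to 33% at p = 40%. There, cluster-robust SEs were within about 2% of the truth. The excess shrinks with correlation because two errors partly cancel, not because the intercept has captured the clustering.

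**Step 3, power.** One patient per aide, 25% versus 15% (risk ratio 0.6, assumed): ln(0.25/0.15) = 0.511, Poisson SE sqrt(1/13 + 1/7.8) = 0.453, actual SE sqrt(0.75/13 + 0.85/7.8) = 0.408.

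- Model-based test: Φ((0.511 - 1.96 × 0.453)/0.408) = 18%.
- Correct SE: Φ(0.511/0.408 - 1.96) = 24%.

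A simulation of the same risk ratio with 1 to 3 patients per aide and an aide SD of 0.2 on the log scale (1,500 runs) gave 25% against 32% with cluster-robust SEs at p = 25%, and 40% against 55% at p = 40%. That aide SD corresponds to a low ICC, p(e^0.04 - 1)/(1-p): 0.014 at p = 25% and 0.027 at p = 40%. The gain would be smaller with stronger clustering.

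**Step 4, count coding.** For pure Poisson counts the Poisson SE is about right (ratio 0.97 to 1.00). For over-dispersed counts, a plain Poisson model without the intercept had type I error of 10% to 16%. With the aide random intercept, as planned, it was 5.0% to 6.2%; with cluster-robust SEs it was 5.4% to 6.2%.

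**The case against.** A reader might infer that Table 1 makes these outcomes yes/no, so that the planned intervals are certainly too wide. The documents do not support this. Table 1 uses the singular, which may only describe what counts as one event. Where it intends a dichotomy, for the 911 questions, it says so. The analysis text speaks of rates, for which Poisson is a standard model. The privacy section says the outcome file will hold "information on hospitalizations and ED visits within 90 days of the start of the intervention", in the plural, so counts may be available. Under that reading the problem disappears. The direction of error is therefore conditional on the coding.

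A reader might also apply the 25% to ED visits and hospitalizations. It belongs to 30-day readmission among Medicare beneficiaries, and the Poisson sentence does not name readmission. No frequency is given for the two outcomes that it does name.

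It is also fair to say that the section is only a brief overview, so silence on the variance does not prove that model-based SEs will be used. The preliminary effectiveness estimates named as a study goal concern the primary outcomes, and power for the patient outcomes is low with either SE at the documented frequency. All of this stands and limits the weight of the point.

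What it does not remove is the gap itself: the coding is open, the readmission model is unnamed, and under one natural coding the stated model has the wrong variance.

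**Conclusion.** The point holds conditionally. If the outcomes are yes/no per patient and model-based SEs are used, the SEs are too large by up to 15% at p = 25%, with 5% to 29% over an assumed p of 10% to 40%. At ICC 0.10 with 2 to 3 patients per aide, the excess at p = 25% falls to roughly 5% to 10% by formula. If events are counted, the planned mixed model is adequate. The patients per aide, the ICC and every frequency except the 25% are assumptions. The error is towards caution, creates no false-positive risk, and leaves the primary and secondary outcomes untouched. This is a low-cost improvement to an exploratory analysis.

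**What to change.** 1. In Table 1, state for ED visit, hospitalization, and 30-day and 90-day readmission whether the variable is any event (yes/no) or the number of events.
2. In Outcome analyses, name one model for all three: log-link Poisson regression with sandwich standard errors clustered on the aide (Stata: `poisson` with `vce(cluster HHA)`). Report a risk ratio for any-event outcomes, or a rate ratio, with follow-up time as the exposure, for counts.

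This is safe under either coding. In the 1,500-run simulations, type I error was 4.5% (p = 25%) and 4.1% (p = 40%) for yes/no outcomes and 4.7% for over-dispersed counts. About 104 aides, or 88 after the planned 15% attrition (104 × 0.85), is enough clusters for the sandwich variance.

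The cost is one Stata option, one sentence in the analysis section and a few words in Table 1. The estimate becomes population-average instead of aide-specific. Under a log link with a random intercept unrelated to arm, the two ratios coincide, so little interpretation is lost. Functional status, which shares the Poisson sentence but is not described as an event, is outside this change and needs its own model.
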